12 MEASUREMENT OF EFFECT

12.1 Response Criteria

The primary endpoint for evaluation of response is established at the 6-month time point. Patients will be evaluated for response based on their ScGVHD evaluation. For the secondary endpoints, other involved organs will be evaluated, but not used in scoring for response to therapy (see appendix P).

12.1.1 ScGVHD will be measured and scored at baseline and every three months from beginning protocol treatment and will be measured by Physiatry. The ROM score will be

based on the composite joint ROM from the three most affected joints for patients with 3 or more affected joints (Appendix M, N). For those patients with fewer than 3 affected joints, the 2 most affected joints or the change in the overall ROM if only a single joint is affected. As there is not currently standardized assessment for ScGVHD, in our experience ROM assessments provide the most reproducible measure of disease progression or improvement in patients with involvement of skin and subcutaneous tissue involving joints. ROM will be measured using the American Academy of Orthopaedic Surgeons Criteria (AAOS, Chicago 1965). Percent change is based on percent change of deficit as compared to baseline. This scoring system has been successfully used in several recently published studies from the NCI evaluating the effects of anti-fibrotic agents on radiation-induced fibrosis[36,37].

As mentioned above, range of motion has been used in other clinical trials as a primary outcome measure, including trials conducted at the NIH Clinical Center studying pentoxifylline [37] and pirfenidone [36] for the treatment of radiation-induced fibrosis. There are several criteria by which ROM may be performed. Our physiatrist will perform the ROM measurements using the American Academy of Orthopaedic Surgeons Criteria (AAOS), which has been used extensively for several decades. However, reproducibility is a potential concern, and we will attempt to minimize this by the use of a single clinician who is experienced in ROM measurement. It is also important to recognize that there are no alternative validated measures of skin fibrosis in ScGVHD [32]. This emphasizes the value of the secondary objective to “establish outcome criteria for the evaluation of ScGVHD using multi-modality objective and subjective assessments, including magnetic resonance imaging, skin scoring, and patient self-reported measures”.

To our knowledge, there is no data on the decrease in ROM typically found in individuals with ScGVHD, but it is dependent on the severity and extent of disease.

12.1.2 **Progression:** defined as one of the following:

12.1.2.1 Joint ROM: decrease of >25% in composite ROM score on 2 consecutive evaluations at least 2 weeks apart, but not greater than 4 weeks apart.

11.1.2.2: Steroid pulse: > 1 steroid pulse per 3 month period (see section for acceptable steroid pulsing guidelines) if administered for ScGVHD.

12.1.3 **Response:** defined one of the following:

12.1.3.1 Joint ROM: increase of >25% in composite ROM score.

12.1.4 **Maximal Response:** Defined as a response with no further improvement over 2 sequential 3-month evaluations.

12.1.5 **Stable Disease:** Does not meet above criteria for progression, response, or maximal response.

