5.3 Duration of Therapy

Patients will be evaluated weekly for side effects for a minimum of one month or until stable dose is achieved. Patients will be evaluated monthly thereafter for safety monitoring and every 3 months for disease response. The primary endpoint assessment will occur at 6 months. Responsive patients will be provided continued treatment for up to 6 months following maximal response up to a maximum of 24 months. While on study, patients will need to return to the clinical center for evaluations at the 1 month, 3 month and 6 month time points, and every 6 months thereafter. Interim evaluations may be done by their primary physician. Patients who progress on treatment will be removed from the study.

In the absence of treatment delays due to adverse event(s), treatment will continue until the primary endpoint (6 months). Patients who are continuing to show a response will be treated up to 2 years or until one of the following criteria applies:

- Disease progression after 8 weeks, or no evidence of response at 6 months,

- Intercurrent illness that prevents further administration of treatment,
- Unacceptable adverse event(s),
- Patient decides to withdraw from the study,
- General or specific changes in the patient's condition render the patient unacceptable for further treatment in the judgment of the investigator,
- Recurrent malignancy
- Inability to comply with study requirements or PI discretion
- Patients requiring additional systemic therapy for control of GVHD will be taken off study after discussion with the PI or LAI.

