and routine infectious disease surveillance as clinically indicated. For patients with serum creatinine levels above the age-adjusted normal limits, an eGFR will be performed.

3. Urinalysis and Lymphocyte Phenotyping TBNK will be performed every 3 months.

4. Complete GVHD evaluation at the NIH will be performed every 3 months. This includes eye evaluation, dermatology assessment, oral assessment, ROM physiatry evaluation, pulmonary function tests (PFTs) if indicated, quality-of-life scales and functional assessment evaluation (including OT evaluation). NIH subspecialty exam (ie. ophthalmology, dentistry) will be employed if clinically indicated. ROM evaluation constitutes the primary study endpoint.

5. Research labs as per appendix C.

11.1.3 End of Study Evaluation:

The following tests and procedures should be performed, if possible, at the time a patient comes off treatment regardless of the reason for coming off treatment, unless the test or procedure has been performed in the last 4 weeks (2 weeks for physical examination and laboratory assessment). This evaluation should be at the NIH.

1. History and physical examination, performance status, ROM and functional assessment, and complete assessment of cGVHD including evaluation by Dermatology, Physiatry, and OT. Other evaluations such as Ophthalmology and Dental if indicated.
2. Laboratory Assessment: Complete blood count, differential and platelet count, Electrolytes, creatinine, calcium, magnesium, phosphorus, SGPT, bilirubin, and urinalysis.
3. MRI of the skin.
4. Pulmonary function tests (if indicated).
5. High resolution CT scan of the chest for patients with BO.
6. Quality-of-Life Scale.
7. Apheresis. (Optional)

At the physician's discretion, patients may be asked to return to the NIH for a one year off treatment evaluation prior to their removal from this study.

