14.4 Analysis of Secondary Endpoints

Secondary endpoints are also important as described elsewhere in the protocol. These include evaluations for toxicity, lung manifestations, percent of patients who are considered as responding or stable from the use of imatinib mesylate, time to progression and time to response, evaluations of tissue or blood samples, MRI results, quality of life, rehabilitative and functional changes. Since this is a pilot study, all secondary endpoints will be evaluated with exploratory intent, using non-parametric techniques and will use data on however many patients are able to provide the necessary information. No patients will be enrolled for the sole purpose of increasing the accrual for evaluation of secondary endpoints. A set of several occupational therapy assessments will also be performed at baseline and at three month time points. Differences from baseline to subsequent time points will be obtained, and these changes will be tested for statistical significance in an exploratory manner most likely using paired non-parametric tests. The changes in assessments will be correlated with clinical measurements as well. Given the limited number of patients to be enrolled on the study, and the fact that these evaluations will all be considered exploratory and secondary, the results will be reported without formal adjustment for multiple comparisons. The results will be noted to be exploratory in any publications in which they are incorporated. Should any interesting findings be identified in this manner, this information may be used to help design future studies for patients with cGVHD.

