Observation	Eligibility	Pretreatment	Labs: weekly x 1 mos; every other week x 6 mos; then monthly	H &P: every other week x 1 mos; then monthly	Q 3 mos	6 Month	Post Study
History & physical exam ¹	X	X		X	X	X	X
Performance status	X	X	X		X	X	X
Body surface area		X			X	X	
CBC, platelets, differential 	X	X	X		X	X	X
PT/PTT, fibrinogen, iron, ferritin, transferrin		X					
Chem 20 panel, For patients with serum creatinine levels above the age-adjusted normal limits, an eGFR will be performed.	X	X	X		X	X	X
Urine/serum pregnancy test (females)		X	X		X	X	
Urinalysis		X			X	X	
Research Labs		X			X	X	
Infectious surveillance- CMV, HSV, HTLV, VZV, EBV		X					
Immunoglobulin levels		X					
Lymphocyte Phenotyping TBNK		X			X	X	X
CT Scan of chest		X					
MRI of skin (ScGVHD)		X [#]				X [#]	X [#]
Skin Biopsy (Skin GVHD)	X	X				X	
Physiatry: ROM & OT Examination	X ^{**}	X			X [*]	X [*]	X [*]
Pulmonary Function Tests		X			X ⁺	X ⁺	X ⁺
Ophthalmology Evaluation		X ⁺			X ⁺	X ⁺	X ⁺
Dental Evaluation		X ⁺			X ⁺	X ⁺	X ⁺
QOL assessment (≥ 18 years)		X			X	X	X
ECHO or MUGA	X						
ECG		X					
HBV, HCV, HIV screening, 24 hour CrCL for patients with an elevated serum creatinine	X						
Apheresis (optional)		X					X

¹H&P to include review of patient diaries to include compliance and toxicity monitoring [#]MRI will not be performed in children who require sedation * Patients with progressive disease will have a repeat evaluation in 2-4 weeks for confirmation of findings. ** Physiatry: ROM Examination only +Only for patients with organ involvement at screening, or otherwise clinically indicated.

18 Appendix C: Research Sample Procedures

Study	Responsible Investigator	Time points	Volume	Notes
PDGFR studies		Baseline, then Q 3 months (blood) Baseline, 6 months (skin biopsy)	See below.	All blood/plasma samples to be received and processed by [name] in the Pre-clinical Services Lab, Building 10 room 12C216., however, PDGRF studies hold the highest priority.
Immune function studies	[name] [contact]	Baseline, then Q 3 months	Quantity and type of specimens to be approved by [name] prior to draw.	All blood/plasma samples to be received and processed by [name] in the Pre-clinical Services Lab, Building 10 room 12C216. *Total samples to be collected include 9-10 CPT tubes, *5-10 mL x 2 in heparin (green top tube), *4ml SST tube (red/yellow rim) and *5-10 mL in EDTA. Samples to be distributed to [name], [name], and [name] Labs via Pre-clinical Lab. †

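### If the 2–4 week repeat ROM exam is missed or late, the 4-week cap in 12.1.2.1 keeps a loss of more than 25% seen again later from counting as progression, and 12.1.5 labels it stable

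*Combined protocol and SAP*

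**What the plan says.** Section 12.1.2.1 requires a "decrease of >25% in composite ROM score on 2 consecutive evaluations at least 2 weeks apart, but not greater than 4 weeks apart". The only other route to progression in 12.1.2 is "> 1 steroid pulse per 3 month period", if given for ScGVHD. Section 12.1.5 defines stable disease by exclusion: "Does not meet above criteria for progression, response, or maximal response".

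On timing, 12.1.1 states that "ScGVHD will be measured and scored at baseline and every three months from beginning protocol treatment", and 11.1.2 that "Complete GVHD evaluation at the NIH will be performed every 3 months". The Appendix B calendar attaches a footnote to the ROM exam in its 3-monthly, 6-month and post-study columns: "Patients with progressive disease will have a repeat evaluation in 2-4 weeks for confirmation of findings". Section 5.3 says that "patients will need to return to the clinical center for evaluations at the 1 month, 3 month and 6 month time points", and six-monthly after that. It does not mention the repeat.

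Section 14.4 lists among the secondary endpoints "percent of patients who are considered as responding or stable from the use of imatinib mesylate, time to progression and time to response".

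**The concern.** The lower limit of 2 weeks guards against measurement noise. The upper limit of 4 weeks does something different: it discards later confirmation, including a loss still present three months on. Because stable disease is the residual category, a patient whose repeat did not take place in the window is counted with the stable patients rather than as unconfirmed or unevaluable.

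A missed or late repeat is foreseeable. Patients are recruited nationwide, a single experienced clinician is meant to take the ROM measurements, and the repeat appears only in a calendar footnote. That footnote is also circular: it is triggered by progressive disease, which cannot be established until the repeat has been done.

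At stake are the percentage responding or stable and the time to progression. Both errors run one way: worsening is either scored as stability or recorded late.

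**Working it through.** The plan gives no figure on this point, so the check is of intervals, followed by an illustrative size.

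**Inputs**
- Loss of more than 25% on two consecutive exams, 14 to 28 days apart (12.1.2.1).
- Scheduled ROM every 3 months (11.1.2, 12.1.1), with a repeat at 2–4 weeks after an exam showing progression (Appendix B).
- Anything else is stable (12.1.5).
- Target of 10 evaluable patients (14.1).
- Assumed, not in the documents: 2 of 10 patients progress, and 25–50% of repeats are missed or late.

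**Step 1: can two scheduled exams qualify?** Three 28-day cycles are 3 × 28 = 84 days (12 weeks). Three calendar months are 365.25 / 4 = 91.3 days (13.0 weeks). Against the 28-day limit, 84 / 28 = 3.0 and 91.3 / 28 = 3.3. Two scheduled exams alone never qualify.

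**Step 2: apply the rule.** Month 3 is day 91 and month 6 is day 183. Losses are 30% unless stated, and the steroid-pulse criterion is taken as not met.

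| Pattern | Gaps (days) | Current rule | Rule proposed below |
|---|---|---|---|
| Days 91 and 183, neither repeated | 92 | Stable | Progression, dated day 91 |
| Day 91, repeat day 112 | 21 | Progression | Progression, dated day 91 |
| Days 91 and 183, only month 6 repeated, day 204 | 92, 21 | Progression, but only from the month-6 pair | Progression, dated day 91 |
| Day 91, late repeat day 127, day 183 not repeated | 36, 56 | Stable | Progression, dated day 91 |
| Days 91 and 183, repeats on days 112 and 204 show a 20% loss | 21, 71, 21 | Stable | Stable |
| First loss day 183, no repeat | none | Stable | Reported separately |

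The two rules classify differently only where a timely repeat is missing. The second row shows that the planned visits give the right answer, and the fifth that a loss which does not confirm stays stable.

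**Step 3: size.** Overstatement in points = 100 × (progressors × probability of no valid confirmation) / 10.
- One chance to confirm (for example, a loss first seen at month 6): 2 × 0.25 / 10 = 0.05 and 2 × 0.50 / 10 = 0.10, so 5–10 points. The same 25–50% of progressions drop out of time to progression.
- Two chances (a loss at month 3 still present at month 6, misses independent): 2 × 0.25² / 10 = 0.0125 and 2 × 0.50² / 10 = 0.05, so about 1–5 points.

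If the same patients tend to miss both repeats, the two-chance figure moves towards the one-chance figure. With one progressor in ten, both ranges halve.

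**The case against.** A reader might infer that the schedule itself turns every sustained loss into stable disease. The documents do not support that. Section 11 names Appendix B as the study calendar, and its footnote provides a repeat whose window matches 12.1.2.1. The two exams intended are the triggering exam and its repeat. A patient followed as planned is classified correctly, and what remains is a missed or late visit. The month-6 exam carries the same footnote, so a loss first seen at month 3 is lost only if both repeats fail. This objection stands, and it limits the point to that case.

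A reader might also infer that the primary result is biased. It is not, by this route: 14.1 analyses ROM change as a continuous measure, with a slope analysis alongside, and neither uses the progression category. The affected endpoints are declared exploratory. A patient wrongly called stable with no response would in any case stop treatment at 6 months under 5.3.

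The size rests on assumed rates. Two ROM progressors in ten already uses the top of the 10–20% that 14.1 allows for drop-out before 6 months from all causes. That criticism is fair, and the ranges should be read as illustrations.

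The absence of the repeat from 5.3 is not in itself a contradiction, since a conditional visit can reasonably sit in the calendar.

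The upper limit does encourage prompt confirmation. That purpose is served by keeping 2–4 weeks as the target visit. It does not require later confirmation to be scored as stability. Appendix P, for patients with a starting lung function score of 10 or more, asks for two tests at least 2 weeks apart and sets no maximum.

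**Conclusion.** The point holds in a limited form. Where the Appendix B repeat is missed or done after 4 weeks, a loss of more than 25% seen again later is not ROM progression and is scored stable, unless a later loss is confirmed within 2–4 weeks or the steroid-pulse criterion is met. This follows from the text without any assumed figure.

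The effect is confined to the percentage responding or stable and the time to progression, and it favours imatinib. Each affected patient is 1 / 10 = 10 points. The expected overstatement of about 1–5 points with two chances to confirm, or 5–10 with one, depends on the assumed progression and missed-repeat rates and, for the lower range, on independent misses. The change is worth making because the present wording gives a definite and wrong classification in a foreseeable case. It does not threaten the primary analysis.

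**What to change.** For endpoint classification only:

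1. In 12.1.2.1, count ROM progression when a decrease of more than 25% is confirmed at the next ROM evaluation at least 2 weeks later, with no upper limit, dated to the first exam. Keep the 2–4 week repeat as the target visit.
2. In 12.1.5, exclude from stable disease any patient whose last ROM exam shows a decrease of more than 25% with no repeat done, and report that patient separately.
3. Do not alter the removal rule in 5.3. Section 12.1.2 is the only definition of ScGVHD progression, and 5.3 relies on that term, so the sponsor should state whether removal uses the same definition as endpoint scoring.
4. Reconcile the visit lists. Section 5.3 has centre visits every 6 months after month 6, 11.1.2 has NIH evaluations every 3 months, and the repeat exam appears only in Appendix B.

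The cost is a few sentences and no visit beyond those in Appendix B. The responding-or-stable percentage may be slightly less favourable, and if removal keeps the present wording, the protocol will hold two definitions that must be clearly labelled.

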5.2 General Concomitant Medication and Supportive Care Guidelines

5.2.1 Steroid therapy.

For patients on systemic steroids, a steroid taper will be attempted 6 to 8 weeks after starting on protocol for those patients responding to therapy. Steroid taper will be performed at a maximal approximate rate of 10% (of starting dose) decrease per week. Once patients are on the equivalent prednisone dose of 0.5 mg/kg/day, taper will consist of decreasing the dose on an every other day schedule. The total decrease should remain equivalent to a maximum of approximately 10% decrease per week as tolerated. For worsening of cGVHD symptoms during steroid taper, a steroid pulse and dose increase will be allowed and subsequent taper attempted. For example, a typical steroid pulse of the equivalent to 1-2 mg/kg for 5-7 days with subsequent taper is acceptable. Steroid pulses require PI or LAI approval. Greater than 1 steroid pulse per 3 month period is considered disease progression. For patients on corticosteroids, consideration will be given to H2 blockade or other gastrointestinal protective agents.

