Patients may drop out due to disease progression, recurrent malignancy, inability to comply with study requirements, unacceptable toxicity, or need for additional systemic therapy for cGVHD, prior to the 6-month evaluation. It is expected that this will be the case in no more than 10-20 percent of patients. In order to allow for this, up to 13 patients will be permitted to be enrolled, but accrual will stop when 10 are evaluable. Patients will only be replaced if they are not evaluable for the ROM evaluation at the 3 month time point for any reason, since this would make the slope estimate impossible to determine (in the absence of intermediate time points, which are not useful to obtain since anti-fibrotic responses are likely to be slow and thus not reflective of any benefit when possible to be identified).

There could be bias due to drop out because of progression, but this is expected to be very limited. In addition to 6-month values, the trial will also obtain intermediate values at 3 months. By having these intermediate values available, estimates from fitting a regression line or from a

'last observation carried forward' technique may be used to try to obtain reasonable substitutes for values not available from those who do not complete 6 months of observation. This type of procedure will be done with appropriate caveats if implemented.

A stopping rule based on the appearance of unresolved grade 3 or any grade 4 toxicity attributable to imatinib will be as follows: if at any time during the trial, a cumulative total of 2 patients experience this level of toxicity, no further patients will be enrolled. This is because the upper one-sided 80% confidence bound on fractions between 2 of 3 and 2 of 10 patients with toxicity extends from 0.38 to 0.93, and as such, this level of toxicity would be consistent with levels clearly considered excessive and which outweigh the potential benefit of the agent in this population.

As this is a one-arm pilot study, there is no control for natural history or regression to the mean, but improvements without the use of treatment are unlikely since this manifestation of GVHD is typically static or progressive and does not remit or improve spontaneously. Nonetheless, if results from this trial look promising, then a randomized study is indicated as the next evaluation.

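### A patient who leaves for additional systemic therapy for sclerotic skin disease can be classified as stable, because section 12.1.2 does not count that therapy as progression

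*Combined protocol and SAP*

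**What the plan says.** Section 12.1.2 lists two ways to progress. The first is measured: "Joint ROM: decrease of >25% in composite ROM score on 2 consecutive evaluations at least 2 weeks apart", with the two evaluations no more than 4 weeks apart. The second is "> 1 steroid pulse per 3 month period", counted only when the pulses are given for ScGVHD. Section 5.2.1 carries the same idea in the treatment rules: "Greater than 1 steroid pulse per 3 month period is considered disease progression".

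Section 12.1.5 defines stable disease by exclusion: "Does not meet above criteria for progression, response, or maximal response". It sets no minimum duration, asks for no follow-up ROM and says nothing about new therapy.

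Additional therapy appears elsewhere, as an exit. Section 5.3 has: "Patients requiring additional systemic therapy for control of GVHD will be taken off study after discussion with the PI or LAI". Section 14.1 gives it as a dropout reason in a list that names disease progression separately: "unacceptable toxicity, or need for additional systemic therapy for cGVHD, prior to the 6-month evaluation". Of all early exits together, section 14.1 says: "It is expected that this will be the case in no more than 10-20 percent of patients".

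Section 14.4 names time to progression and the "percent of patients who are considered as responding or stable from the use of imatinib mesylate" among the secondary endpoints. It calls all of them exploratory and bases them on the patients who can supply the data.

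**The concern.** The protocol already accepts that escalating treatment can mark progression: repeated steroid pulses for ScGVHD count, whatever the ROM shows. Adding a new systemic agent for the same disease is also an escalation, and it does not count. Because stable disease is the remainder, a patient who needed that agent falls into the favourable group.

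Section 14.1 describes this manifestation as usually static or progressive. A patient who gains nothing from imatinib may therefore have a nearly unchanged ROM, which is the pattern the residual category absorbs. Section 14.4 says that findings on secondary endpoints may help to design later studies, so a responding-or-stable rate that includes such patients could be carried forward as evidence of disease control.

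**Working it through.** **1. The plan's own figures.** The plan gives no expected value for the responding-or-stable rate, so there is none to reproduce. Its primary power statement does reproduce: with n = 10, a 1.0 SD change and two-sided alpha 0.05, the noncentral t (9 degrees of freedom, noncentrality √10 = 3.16) gives power 0.803, against the stated 80%. That analysis does not use the response categories.

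**2. The definitions applied.** Take a patient who starts another systemic drug and leaves, with no ROM gain above 25%.

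| Situation at exit | 12.1.2 met? | Class as written | Effect on the 14.4 rate |
|---|---|---|---|
| ROM loss >25%, confirmed | Yes | Progression | Unfavourable |
| More than one steroid pulse in 3 months for ScGVHD | Yes | Progression | Unfavourable |
| Follow-up ROM within the limits; drug added for ScGVHD | No | Stable | Favourable |
| First ROM loss >25%, no confirming ROM; drug added for ScGVHD | No | Stable | Favourable |
| No post-baseline ROM | No | Stable by 12.1.5 alone | Most naturally dropped under the available-data rule |

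Rows 3 and 4 are the problem. These patients will often have data: ROM is measured every 3 months, and section 11.1.3 plans a ROM, if possible, when treatment stops for any reason. The available-data rule does not then remove them.

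**3. Size per patient.** Let N be the number in the rate, k the number in rows 3 and 4, and g the number of other progressions. Assume that everyone else is responding or stable.

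- As written: (N − g)/N
- Row 3 and 4 patients dropped: (N − g − k)/(N − k)
- Row 3 and 4 patients counted as progression: (N − g − k)/N
- Difference between the first and the third: k/N

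| N | g | k | As written | Dropped | As progression |
|---|---|---|---|---|---|
| 10 | 0 | 1 | 100% | 9/9 = 100% | 90% |
| 10 | 0 | 2 | 100% | 8/8 = 100% | 80% |
| 10 | 2 | 1 | 80% | 7/9 = 78% | 70% |
| 10 | 2 | 2 | 80% | 6/8 = 75% | 60% |

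Each such patient moves the rate by 1/10 = 10 points at N = 10, or 1/13 = 7.7 points at N = 13. For scale, the binomial standard error at n = 10 is √(0.7 × 0.3/10) = 14.5 points for a true rate of 70%, and √(0.5 × 0.5/10) = 15.8 points for 50%.

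**4. How many patients.** Section 14.1 puts all early exits at 10-20% at most, which is 1-2 of 10 or 1.3-2.6 of 13. If all were of the row 3 or 4 kind, the difference would be 10-20 points. The share that is of this kind is not stated. If it were half (an assumption for illustration), the difference would be 5-10 points.

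**The case against.** The strongest reply is that the gap is narrow and the endpoints are exploratory. Most of its parts stand.

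- **No post-baseline ROM.** A reader might infer that a patient never measured after baseline counts as a success. Section 12.1.5 alone would allow that, but section 14.4 restricts secondary analyses to patients with the needed data, and section 12.1 bases response on the ScGVHD evaluation. The natural reading drops this patient.
- **Very early exits.** Section 14.1 replaces patients who are not evaluable for ROM at month 3, and section 14.4 does not say whether replaced patients enter the rate. The documents do not support treating a month-2 exit as a counted success.
- **Other organs.** Section 5.3 speaks of GVHD generally, and section 12.1 keeps other organs out of the response score. Therapy added for lung, gut or liver disease is not evidence that imatinib failed in the skin.
- **Other exits.** Toxicity, recurrent malignancy and inability to comply are not skin progression, so leaving them out of section 12.1.2 is not an error. Tolerability has its own rule in section 14.1.1.
- **Time to progression.** Whether to censor or count an event at new therapy is a recognised choice, and the plan does not state its censoring rule. This stands in part: such a patient is not turned into a success. But censoring someone because the skin disease needed another drug is informative, and it sits badly with counting repeated steroid pulses as an event.

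None of this reaches the patient with a follow-up ROM who leaves for additional therapy for ScGVHD and meets neither criterion. For that patient the text gives a definite class, stable.

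**Conclusion.** The point holds in this limited form. It is a stated rule that gives a wrong result for one kind of patient, not merely a missing detail. The effect is 10 points on the responding-or-stable rate per affected patient at n = 10, always in the favourable direction, plus a lost event in time to progression.

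A reader might infer that the rate is inflated by the full 10-20 points. The documents do not support that. The 10-20% is a ceiling on exits for all reasons; disease progression is among those reasons, and patients who meet section 12.1.2 are never scored stable. The figure is an upper bound under the plan's own dropout expectation, and the true effect could be a fraction of one patient in ten, or nothing if no one leaves in this way.

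The size rests on two assumptions: that affected patients have a follow-up ROM and stay in the rate, and that n is about 10. The primary ROM analysis, the tolerability rule and the stopping rule do not depend on these categories. This is a modest correction to exploratory secondary endpoints.

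**What to change.** Make three changes, for analysis only:

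1. **Section 12.1.2:** count the start of additional systemic therapy for ScGVHD, not for other organs, as progression, dated at the start of that therapy.
2. **Section 12.1.5:** require a post-baseline ROM (month 3, month 6 or the section 11.1.3 exit visit) before a patient is called stable.
3. **Section 14.4:** report patients without a post-baseline ROM as not evaluable, and show the rate a second time with all treated patients in the denominator.

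The cost is a sentence or so in each place. No new visit is needed, since the exit ROM is already planned. Section 5.5 already has the reason for removal recorded; that entry would need to say whether the added therapy was for ScGVHD. Patient care does not change, because these patients already leave under section 5.3. The reported responding-or-stable rate may be slightly less favourable.
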